10.6 Investigator reporting to the FDA

Adverse drug reactions that are **serious, unlisted/unexpected, and at least possibly associated to the drug**, and that have not previously been reported in the Investigators brochure, or reference safety information document should be reported promptly to the FDA in writing by each investigator/physician engaged in clinical research. A clear description of the suspected reaction should be provided along with an assessment as to whether the event is drug or disease related.

The investigator/physician shall notify the FDA by telephone or by fax of any unexpected fatal or life threatening experience associated with the use of the drug as soon as possible, but no later than 7 calendar days after the sponsors initial receipt of the information. Each phone call or fax shall be transmitted to the FDA new drug review division in the Center for Drug Evaluation and Research or the product review division in the Center for Biologics Evaluation and Research that has responsibility for review of the IND if applicable.

10.7 Reporting of adverse drug reactions and other safety information to study supporter

All suspected AEs and other safety information associated with the administration of NewGam have to be reported to:

Email: [contact]

[contact]

Serious adverse drug reactions have to be reported immediately by fax or email (within 24 hrs). Non-serious adverse drug reactions and other safety information should be reported to Octapharma, if possible, upon recognition but no later than 10 days.

10.8 Report of adverse events to the institutional review board

The principal investigator is required to notify the Sutter Health Institutional Review Committee (SHCIRC) of a serious adverse event according to institutional policy.

10.9 Reporting of adverse drug reactions and other safety information to study sponsor

Octapharma shall notify the Investigator via an IND Safety Report of the following information:

- Any AE associated with the use of study drug in any studies involving Newgam 10% that is both serious and unexpected.
- Any finding from tests in laboratory animals that suggests a significant risk for human subjects including reports of mutagenicity, teratogenicity, or carcinogenicity.

10.10 Adverse event updates

The investigator must keep copies of all AE information, including correspondence with Octapharma and the SHCIRC, on file.

The investigator shall notify the SHCIRC promptly of any new serious and unexpected AE(s) or significant risks to subjects.

11.0 IND ANNUAL REPORTS

The conduct of the study will comply with all FDA safety reporting requirements.

11.1 IND annual reports

If the FDA has granted an IND number, it is a requirement of 21 CFR 312.33, that an annual report is provided to the FDA within 60-days of the IND anniversary date. 21 CFR 312.33 provides the data elements that are to be submitted in the report. The Annual Report should be filed in the study's Regulatory Binder, and a copy provided to Octapharma as a supporter of this study as follows:

Octapharma Pharmazeutika Produktionsges.m.b.H
attn: [name] (Head Int. Drug Regulatory affairs)
[name]
[name]

All AE reports must include the patient number, age, sex, weight, severity of reaction (mild, moderate, severe), relationship to study drug (probably related, unknown relationship, definitely not related), date and time of administration of test medications and all concomitant medications, and medical treatment provided. The investigator is responsible for evaluating all adverse events to determine whether criteria for "serious" and as defined above are present.

2.0 12.0 RESPONSE CRITERIA

The MMSE, CDR-SB, and ADAS-cog are scheduled to occur at 4, 8, 12, 16, 20, 24, 36, 48, and 60 months after Visit 1.

3.0 13.0 PROTOCOL DEVIATIONS

When an emergency occurs that requires a deviation from the protocol for a subject, a deviation will be made only for that subject. A decision will be made as soon as possible to determine whether or not the subject (for whom the deviation from protocol was effected) is to continue in the study. The subject's medical records will completely describe the deviation from the protocol and state the reasons for such deviation. In addition, the Investigator will notify the SHCIRC in writing of such deviation from protocol.

Non-emergency minor deviations from the protocol will be permitted with approval of the principal investigator.

14.0 DATA RECORDING, RETENTION, AND MONITORING

14.1 Data entry and maintenance

Investigator responsibilities are set out in the ICH guideline for Good Clinical Practice (GCP) and in the US Code of Federal Regulations.

Study personnel will construct case report forms (CRFs), record all study data onto the CRFs and enter the data into a 21 CFR Part 11 compliant database.

14.2 Study records retention

The investigator must ensure that the records and documents pertaining to the conduct of the study and the distribution of the study drug, that is copies of CRFs and source documents (original documents, data, and records [e.g., hospital records; clinical and office charts; laboratory notes; memoranda; subject's diaries or evaluation checklists; SAE reports, pharmacy dispensing records; recorded data from automated instruments; copies or transcriptions certified after verification as being accurate copies; microfiches; photographic negatives, microfilm, or magnetic media; x-rays; subject files; and records kept at the pharmacy, at the laboratories, and at medico-technical departments involved in the clinical study; documents regarding subject treatment and study drug accountability; original signed informed consents, etc.]) be retained by the investigator for as long as needed to comply with national and international regulations (generally 2 years after discontinuing clinical development or after the last marketing approval). The investigator agrees to adhere to the document/records retention procedures by signing the protocol.

14.3 Data monitoring committee

The Data Monitoring Committee (DMC) will be composed of independent reviewers who will meet to review the efficacy and safety data and determine a risk/benefit analysis in this subject population. The purpose of the DMC is to advise on serious safety considerations, lack of efficacy, and any other considerations within the charge to the Committee. The DMC may request additional meetings or safety reports as deemed necessary upon discussion with the investigator or Octapharma and its representatives. The DMC may stop the study following review of results from the interim analysis.

15.0 STATISTICAL ANALYSIS

15.1 Primary endpoint

The aim of the primary efficacy analysis is to demonstrate an advantage for subjects treated with IVIG over subjects treated with placebo at the end of the study as measured by change in ventricular volume. The primary efficacy analyses will be performed on the intent-to-treat (ITT) population. The ITT population is defined as all subjects who were randomized, received three or more infusions, and had a brain MRI at baseline and at 24 months.

Annualized percent change in total ventricular volume (APCV) is the primary biomarker of interest. Brain MRI will be obtained at baseline, 12 months, 24 months, 36 months, 48 months, and 60 months. Differences between the IVIG and placebo group at month 12, 24, 36, 48, and 60 will be analyzed using a 2 x 2 analysis of variance. Participants will also be classified as early MCI (EMCI) if baseline CDR-SB is less than 1.5, and late MCI (LMCI) if CDR-SB is greater than or equal to 1.5.

Treatment (IVIG, placebo), MCI status (EMCI, LMCI), and the treatment X MCI status interaction will be included in the model. If the interaction is statistically significant ($p < 0.05$), MCI status will be stratified and differences in APCV between the groups compared within each stratum.

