7.0 EVALUATIONS BY VISIT

The overall summary of study activities by visit is provided in Appendix C at the end of the document.

Screening procedures at visit 1 will take place up to 28 days prior to Visit 2 (Day 1) dosing. Screening labs and assessments will be performed during the screening period. A brain MRI will be obtained as standard of care within 6 months prior to the screening period. The first dose of study drug is administered on Day 1. Visits 2 through 6 have a ± 1 day window and occur every 14 days over two months. The investigator will determine if a subject is suitable to continue following the missed infusion. Visits 7 through 12 (Month 4 through Month 24) have a ± 7 day window. Visits 13 through 15 (Month 36 through Month 60) have a ± 14 day window).

All study screening data from Visit 1 including laboratory results must be reviewed for study eligibility prior to receiving first dose of study drug. Visit 2 physical exams and neurological exams prior to infusion may occur within 72 hours prior to the first infusion. Prior to infusion, a review of concomitant medications and AEs takes place to ensure that no excluded medications have been added or medication discontinued or dose changed that were required to have been stable. If the subject continues to be eligible for enrollment, the subject will be randomized, infused with study medication and will remain in the infusion clinic for at least 4 hours following the start of the infusion for safety assessments on Visit 2 (Day 1).

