7.2 VISIT 2: Day 1 – First Infusion

The investigator will confirm that subjects are still eligible by reviewing all screening data. Subjects who no longer meet criteria will not be eligible for enrollment in the study.

7.2.1 Pre-dose:

- Confirm that subjects continue to meet inclusion/exclusion criteria
- Assess and record AEs
- Record concomitant medications
- Record vital signs
- Perform physical and neurological examinations (may occur within 72 hours prior to first infusion)
- Complete randomization
- The unblinded pharmacist will prepare the study drug according to the preparation instructions in Section 5.7 and will deliver the study drug to the blinded infusion administration site.

7.2.2 Study drug infusion:

- Subjects will be given the option of prophylaxis oral acetaminophen, diphenhydramine, or both 15-30 minutes prior to infusion
- Measure blood pressure, pulse rate, temperature and respiratory rate within 15 minutes prior to start of the infusion
- Administer study drug to the subject by intravenous infusion

7.2.3 Following initiation of infusion:

- Measure blood pressure and pulse rate at 15, 30, 60 and every 30 minute mark for the duration of the infusion
- Measure blood pressure, pulse rate, temperature and respiratory rate immediately post dose and prior to leaving the clinic
- Assess infusion site post infusion
- Assess and record AEs
- Subjects will remain in the clinic for at least one hour following the completion of the infusion. The subjects may leave the clinic after the observation period if the subject is medically stable.

7.3 VISIT 3 (Day 14 -Second Infusion) through VISIT 6 (Day 56 – Fifth Infusion)

- Assess and record AEs
- Record concomitant medications
- Record vital signs
- If there is any abnormality of vital signs or clinical concerns during infusion visit, the principle-investigator or sub-investigator will be paged in order to perform a clinical assessment.
- The unblinded pharmacist will prepare the study drug according to the preparation instructions and will deliver the study drug to the blinded infusion administration

7.3.1 Study drug infusion:

- Subjects will be given the option of prophylaxis oral acetaminophen, diphenhydramine, or both 15-30 minutes prior to infusion
- Measure blood pressure, pulse rate, temperature and respiratory rate within 15 minutes prior to start of the infusion
- Administer study drug to the subject by intravenous infusion

7.3.2 Following initiation of infusion:

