7.13 Early termination from the study

Every attempt should be made to follow each subject through the final visit 12, and subsequently visit 15 of the extension study. In the event of early withdrawal from the subject for any reason, an Early Termination Visit should be completed for criteria of withdrawal. If the subject withdraws due to an AE, every attempt should be made to follow the subject until the AE resolves or until the investigator deems that the AE is stable or determined the AE to be chronic. All SAEs will continue to be followed until the end of the study (Visit 12, 15, or ET visit) or until the SAE has resolved or the investigator deems the event to be stable or chronic.

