8.0 CONVERSION TO ALZHEIMER DISEASE

Patients who convert to AD will have the choice of remaining in the study on a modified follow-up visit schedule, or may withdraw from the study. Depending on when the conversion occurs, the subjects will be asked to complete the following:

- Complete all Visit 7 study activities described above
- Complete only the following for Visit 8:

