 1. HIV-I & II, HCV, HBV, B19, HAV
 2. Adverse events and Concomitant Meds
- Complete all Visit 9 study activities described above
- Subjects will not attend Visit 10 and Visit 11
- Complete all Visit 12 study activities
- Complete all Visit 13, 14, and 15 study activities (optional)

Patients who convert to Alzheimer Disease will be followed for safety reasons, to determine rate of conversion between groups, and to track any continued changes in ventricular volume between the 0.4 g/kg NewGam or 0.9% saline solution (placebo) groups.

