9.0 WITHDRAWAL AND REPLACEMENT OF SUBJECTS

9.1 Criteria for subject withdrawal

In accordance with the Declaration of Helsinki and other applicable regulations, a subject has the right to withdraw from the study at any time and for any reason. If a subject requests or decides to withdraw, every attempt will be made to complete an early termination visit.

The investigator has the right to withdraw subjects from the study if a subject:

- Is in significant violation of the protocol
- Experiences an intolerable AE or SAE
- Is non-compliant
- Withdrawal of consent
- Lost to follow up
- Death

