9.2 Replacement of subjects

Subjects screened but not randomized will be replaced. Subjects withdrawn after receiving the third infusion will not be replaced but will be followed if they provide consent.

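### The population that Section 15.1 calls ITT is an evaluable set: it requires three or more infusions and a month-24 MRI, both settled after randomisation

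*Combined protocol and SAP*

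**What the plan says.** Section 15.1 states that the primary efficacy analysis uses the intent-to-treat population, and defines it as "all subjects who were randomized, received three or more infusions, and had a brain MRI at baseline and at 24 months". The outcome is annualized percent change in ventricular volume (APCV), compared at months 12, 24, 36, 48 and 60.

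Other sections determine who can meet that definition:

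- Section 7.2.1 lists "Complete randomization" among the Day 1 pre-dose steps. The schedule in 22.1 puts the third infusion on Day 28.
- Section 7.0, on missed infusions: "The investigator will determine if a subject is suitable to continue following the missed infusion".
- Section 9.1 lets the investigator withdraw a subject who "Experiences an intolerable AE or SAE".
- Section 8.0 says that converters to AD "will have the choice of remaining in the study on a modified follow-up visit schedule, or may withdraw from the study". Those who stay are asked to "Complete all Visit 12 study activities", which include an MRI.
- Section 7.13: "Every attempt should be made to follow each subject through the final visit 12".
- Section 9.2: "Subjects withdrawn after receiving the third infusion will not be replaced but will be followed if they provide consent". It does not say what happens to randomised subjects who leave before the third infusion.

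For the cognitive endpoints, Section 15.2.2 plans mixed models on every observation available. The primary endpoint has no counterpart to this, no stated missing-data method and no analysis of all randomised subjects.

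**The concern.** Readers take ITT to mean every randomised subject, analysed as assigned. Here two of the entry conditions are met or failed after assignment: the infusion count about four weeks later, and the scan two years later. A result reported as ITT would describe only subjects who tolerated at least three infusions and were scanned at month 24. If the reasons for failing those conditions differ by arm and are related to ventricular change, the comparison is no longer protected by randomisation.

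The rule also discards usable data. Read literally, a subject with a month-12 scan but no month-24 scan is left out of the month-12 comparison too. The schedule puts an MRI in a combined month-24/early-termination column, but 15.1 does not say whether an early-termination scan counts as the month-24 scan.

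Section 17.0 calls the study exploratory. Even so, 15.1 sets out to show that IVIG is better on this set, and 17.0 expects the results to inform an expansion or a larger trial.

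**Working it through.** **1. When each condition is settled**

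| Condition in 15.1 | When settled | Relative to randomisation |
|---|---|---|
| Baseline MRI | Screening (7.1), or up to six months before screening (7.0) | Before, on either text |
| Three or more infusions | Day 28 at the earliest (22.1) | After |
| Month-24 MRI | Visit 12 (7.9) | After |

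Only the last two are at issue. Sections 7.13 and 8.0 make missing scans less likely, but neither returns an excluded subject to the analysis. A subject with two infusions and a month-24 scan is still out.

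**2. The plan's own figure**

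No number in the plan is attached to this definition. Section 16.0 gives 82% power with 25 per arm for a 120-unit difference (two-sided 0.05), but no SD, so the 82% cannot be reproduced. Solving a two-sample t-test for the SD gives 144.6 units, or an effect of 120/144.6 = 0.83 SD. I use this only as a scale. At 0.83 SD, equal loss in both arms would leave power of 76.7% with 22 per arm and 72.5% with 20. Section 16.0 makes no allowance for loss.

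**3. Bias and type I error under assumed loss**

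The documents give no loss rate. Let p1 and p0 be the fractions excluded in the two arms, and s the amount, in SD, by which excluded subjects lie above their arm's mean. With no true effect:

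- bias b = p1·s/(1 − p1) − p0·s/(1 − p0)
- noncentrality = b / √(1/n1 + 1/n0), with n1 + n0 − 2 degrees of freedom
- type I error = probability that a noncentral t exceeds the two-sided 5% limits.

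This is a two-group approximation to the treatment contrast, with 25 randomised per arm and no replacement.

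Worked case, 5 versus 0 of 25 with s = 1: b = 0.2/0.8 = 0.25 SD; noncentrality = 0.25/√(1/20 + 1/25) = 0.833 on 43 degrees of freedom; type I error 12.9%.

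| Excluded (arm versus arm) | s | Bias (SD) | Type I error |
|---|---|---|---|
| 5 vs 5 of 25 | 1 | 0 | 5.0% |
| 5 vs 0 of 25 | 0 | 0 | 5.0% |
| 1 vs 0 of 25 | 1 | 0.04 | 5.2% |
| 2 vs 0 of 25 | 1 | 0.09 | 6.0% |
| 3 vs 0 of 25 | 0.5 | 0.07 | 5.6% |
| 3 vs 0 of 25 | 1 | 0.14 | 7.4% |
| 20% vs 10% | 0.5 | 0.07 | 5.6% |
| 20% vs 10% | 1 | 0.14 | 7.3% |
| 5 vs 0 of 25 | 1 | 0.25 | 12.9% |

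The direction depends on the arm. Losing fast-enlarging subjects from IVIG flatters IVIG; losing them from placebo does the opposite.

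**4. Loss through conversion**

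Section 1.0 cites, from other cohorts, about 15% conversion per year and 60 of 192 over 1.5 years. Over two years these give 1 − 0.85² = 27.8% and 1 − (1 − 60/192)^(2/1.5) = 39.3%. If a quarter to a half of converters left, the loss would be 6.9% (0.25 × 27.8%) to 19.7% (0.5 × 39.3%) per arm.

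- With no treatment effect, both arms lose converters alike. Simulation (100,000 trials per case, assumed correlation 0.4–0.8 between conversion liability and APCV) gave type I error of 4.9–5.1%.
- Suppose that IVIG lowered conversion to 20–28% against 39%, half of converters left, and the correlation was 0.6. A true 0.83 SD benefit was then estimated at 0.78–0.81 SD, an understatement.

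**The case against.** The strongest case on the other side is that the set is openly defined, the study calls itself exploratory, and its safeguards keep differential loss small. Much of this stands.

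- **Blinding.** The investigator who decides on continuation after a missed infusion is blinded (6.5), which limits discretionary selection by arm. It does not prevent loss driven by adverse events or progression.
- **Follow-up.** Section 7.13 asks that every subject be followed to Visit 12, with no infusion condition, and 8.0 keeps converters' month-24 MRI. No extra follow-up rule is needed. These provisions reduce missing scans but do not change who is analysed.
- **The infusion condition.** The documents give no reason to link early missed infusions to two-year ventricular change, and loss unrelated to outcome leaves type I error at 5.0%. The outcome-related concern therefore rests mainly on the month-24 scan.
- **Size.** The 12.9% requires all five losses in one arm with a 1 SD shift. One or two such losses give 5.2% or 6.0%.
- **Conversion rates.** The 28–39% comes from other cohorts, whereas this trial excludes moderate or severe atrophy (4.2). A reader might instead take Amendment 8's remark about a single conversion at year 2 as evidence of a low rate, but that remark covers the early-MCI stratum only.

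None of this makes the set ITT, and nothing elsewhere in the documents repairs the definition.

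**Conclusion.** The concern holds as a mislabelled primary population with no missing-data rule. The label is wrong on the face of the current text, whatever the loss turns out to be. The rule also excludes randomised subjects who have usable scans, while the cognitive endpoints use theirs.

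A reader might infer that the primary test is inflated, or tilted towards IVIG. The documents do not support either reading. With equal or outcome-unrelated loss, type I error stays at about 5%. Under arm-specific, outcome-related loss of one to three of 25 with a 1 SD shift, it is about 5.2% to 7.4%; 12.9% is an extreme. If IVIG reduces conversion, losing converters would tend to hide benefit. All of these figures assume the loss pattern, 25 randomised per arm, no replacement and a two-group approximation.

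This should be corrected before any result is reported as ITT. It does not by itself invalidate the trial.

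**What to change.** 1. Define ITT as all randomised subjects analysed as assigned, with no infusion-count or month-24-scan condition. Include anyone who leaves before the third infusion, whether or not Section 9.2 leads to a replacement.
2. State one primary analysis: the treatment contrast in APCV at month 24, matching the 24-month objective in 2.1. Use a linear mixed model of the kind planned in 15.2.2, with treatment, MCI status, their interaction, visit and treatment by visit. Use all scheduled and early-termination scans through month 24, and compute APCV from each subject's actual baseline-to-scan interval. Treat months 36–60 as secondary, and at each time point include every subject with a scan.
3. Reconcile Sections 7.0 and 7.1 on when the baseline MRI is taken, because the interval depends on it.
4. Add a tipping-point sensitivity analysis by arm, for example shifts of 0 to 1 SD, that covers subjects with no post-baseline scan.
5. Keep the present set as a supportive analysis named evaluable, and report exclusions by arm and reason.

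The cost is protocol and SAP wording and some modelling, with no new visits or scans. There are three downsides: partly dosed subjects may slightly dilute the estimate, annualised values over short intervals are noisier, and subjects with no post-baseline scan enter only through the sensitivity analysis. Timing also matters. Amendment 8 already cites year-2 conversions and Amendment 9 records a 2016 approval, so this is a late change and must be labelled as one. If month-24 data have been examined, report the new analysis alongside the one now in 15.1 and state when it was specified.

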In July 2009, Fillit et al [10] published a retrospective analysis of the risk of AD and related disorders in people ≥ 65 with a prior history of one or more IVIG treatments for indications other than AD. Cases were matched to controls on age, gender, and risk factors for AD and related disorders. This study analyzed an approximate 4-year period and demonstrated that previous treatment with IVIG was associated with a 42% lower risk of developing AD and related disorders.

The potential protective effect of IVIG against AD could best be utilized in persons identified to be at greatest risk for developing AD prior to the development of advanced disease and neuropathology. Persons with a-MCI have been identified a group at high risk of progressing to AD with a conversion rate of approximately 15% per year. [11, 12] Vermuri used data from the Alzheimer Disease Neuroimaging Initiative including CDR-SB and MMSE to assess disease progression (while investigating potential biomarkers, MRI and CSF) of AD and demonstrated that 60 of the 192 subjects with a-MCI converted to AD over 1.5 years; i.e., annual conversion rate from a-MCI to AD of 20.8% [13].

This study will investigate treating persons with a-MCI with IVIG (NewGam 10%) 0.4g/kg every 14 days over the course of three months with the intent of showing differences in brain MRI volume, cognition, and conversion to AD when compared with placebo after 24 months. We chose this dose of IVIG based on recent evidence from Relkin [8] who showed that this may be an optimal IVIG dose for reduction of brain atrophy in patients with AD. Furthermore, Fillet [10] demonstrated a lower risk of AD in patients who had received only one treatment of IVIG.

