2.0 STUDY OBJECTIVES AND ENDPOINTS

2.1 Primary objective

This randomized double-blinded study will evaluate the efficacy of intravenous immunoglobulin (NewGam 10%) in patients with a-MCI over 24 months after the first infusion.

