2.2 Secondary objective

Additionally, this randomized double-blinded study will evaluate the efficacy of intravenous immunoglobulin (NewGam 10%) in patients with a-MCI over 36 months, 48 months, and 60 months after the first infusion.

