2.3 Primary endpoint

- Change in ventricular volumetric as measured by MRI at baseline, 24 months, 36 months, 48 months, and 60 months following the first infusion of either 0.4 g/kg NewGam or 0.9% saline solution (placebo) every 14 days x 5.

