3.3 Estimated study duration

The duration of each study subject is approximately 24 months, including one screening visit over a period of approximately 28 days, 5 days of infusions over a 2-month period of time, and follow-up visits at 4, 8, 12, 16, 20, and 24 months after the first infusion. Subjects will be given the option to continue study follow-up visits at 36, 48, and 60 months after the first infusion.

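### Month 24 is implied as the primary time point, but sections 2.3, 15.1 and 16 each point elsewhere and no passage ranks the visits

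*Combined protocol and SAP*

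**What the plan says.** These parts of the plan point to month 24:

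- Section 1.0 states the intent as showing "differences in brain MRI volume, cognition, and conversion to AD when compared with placebo after 24 months".
- Section 2.1 sets the primary objective as efficacy "in patients with a-MCI over 24 months after the first infusion". Section 2.2 makes a separate, secondary objective of efficacy "in patients with a-MCI over 36 months, 48 months, and 60 months after the first infusion".
- Section 3.3 puts study duration at about 24 months and makes the rest optional: "Subjects will be given the option to continue study follow-up visits at 36, 48, and 60 months after the first infusion".
- Section 7.13 asks sites to "follow each subject through the final visit 12, and subsequently visit 15 of the extension study". The Appendix C footnotes likewise separate the two-year study from a three-year extension.
- The section 15.1 analysis set requires an MRI at baseline and at 24 months, and at no later visit.
- Section 17 reads the result at two years.

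These parts do not agree with that:

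- Section 2.3 gives the primary endpoint as "Change in ventricular volumetric as measured by MRI at baseline, 24 months, 36 months, 48 months, and 60 months following the first infusion".
- Section 15.1 aims to "demonstrate an advantage for subjects treated with IVIG over subjects treated with placebo at the end of the study", then says "Differences between the IVIG and placebo group at month 12, 24, 36, 48, and 60 will be analyzed using a 2 x 2 analysis" (an ANOVA). Month 12 is in this list but not in section 2.3.
- Section 16, headed as power for the primary endpoint, refers to month 26.

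**The concern.** The primary endpoint list in section 2.3 contradicts the division of objectives in sections 2.1 and 2.2. The aim in section 15.1 does not settle the matter. Its end-of-study wording is not defined for efficacy, and the only gloss, in section 10.1 for adverse events, allows visit 12 (month 24), visit 15 (month 60) or early termination. No passage ranks the visits or controls multiplicity across them. Nor does any passage say whether a comparison within early or late MCI, made after a significant interaction, may stand in for the overall comparison.

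One reader can report month 24 as the primary result. Another can report month 60, or the best of four or five visits, and cite section 2.3 or 15.1. The later visits are optional, so they will probably rest on fewer subjects and can give a different answer.

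**Working it through.** **1. The time points side by side**

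| Section | Months |
|---|---|
| 2.1 primary objective | 24 |
| 2.2 secondary objective | 36, 48, 60 |
| 2.3 primary endpoint | 24, 36, 48, 60 |
| 15.1 aim | end of study, no month given |
| 15.1 analysis set | baseline and 24 |
| 15.1 tests | 12, 24, 36, 48, 60 |
| 16 power | 26 |
| 17 read-out | two years |

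Section 7.0 gives windows of ±7 days at month 24 and ±14 days at month 36. Month 26 is about 61 days after month 24 and falls in neither window.

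**2. The plan's own power figure**

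Section 16 states 25 per arm, a difference of 120 units, two-sided 0.05 and 82% power. It gives no SD, so 82% can be neither reproduced nor called wrong. Solving backwards with the normal approximation, power = Φ(120 / (SD × √(2/25)) − 1.96). For 82% the bracket must equal 0.915, so SD = 120 / (2.875 × 0.2828) ≈ 147.6, a standardised difference of 0.81. The noncentral t gives SD 144.6 and 0.83.

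**3. False positives if a win at any listed visit counted**

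The plan neither states nor excludes this rule. The upper reference is independence: 1 − 0.95⁴ = 18.5% for four visits and 1 − 0.95⁵ = 22.6% for five. Repeated scans in the same subjects are positively correlated, so the following model was simulated:

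- 50 subjects, 25 per arm, four-cell ANOVA with 46 error df, treatment main effect tested at 0.05 at each visit.
- APCV at year t = slope + (e_t − e_0)/t, with slope SD 1 and the baseline error e_0 shared by all visits.
- Assumed scan-error SD s of 0.25, 0.5 or 1, and an assumed early-MCI share of 52, 32 or 20%.

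The correlation between years t and u is (1 + s²/(tu)) / √[(1 + 2s²/t²)(1 + 2s²/u²)]. For s = 0.25, 0.5 and 1 this is 0.95, 0.85 and 0.67 between months 12 and 60, and 0.99, 0.96 and 0.86 between months 24 and 60.

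| Assumption (true null) | Month 24 only | Any of 4 (2.3) | Any of 5 (15.1) |
|---|---|---|---|
| Random slopes, full retention (40,000 replicates) | 4.8–5.0% | 5.9–9.4% | 6.9–12.0% |
| Same, retention 80/65/50% at months 36/48/60 (20,000 replicates; early-MCI share 52%) | – | 10.8–12.1% | 11.7–14.6% |
| Weaker structures: equal correlation or AR(1), 0.5 or 0.7 | – | 13.0–16.8% | 14.8–20.3% |

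If a win within one MCI stratum after a significant interaction also counted, the five-visit, full-retention range would become 9.7–18.6%.

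**4. How often months 24 and 60 would disagree**

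The true effect was set to give 82% power at month 24 (standardised difference 0.83, noncentrality about 2.94) and held constant on APCV.

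| Scan-error SD | 0.25 | 0.5 | 1 |
|---|---|---|---|
| Disagree on p < 0.05, full retention | 3.2% | 6.6% | 12.5% |
| Disagree, retention 80/65/50% | 37.9% | 35.9% | 30.9% |
| Month-60 power, retention 80/65/50% | 49% | 51% | 61% |

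A smaller run with separate code (4,000 replicates) gave 29–36% disagreement under the assumed retention, so about a third is a fair summary.

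**The case against.** The strongest reply is that month 24 is already identified: the objectives, the duration, the analysis set and the read-out all agree on it. On that view section 15.1 lists five visits only because section 15.2 has no whole-sample MRI analysis to serve the secondary objective, and month 12, absent from section 2.3, supports that reading. Section 2.3 could itself be read as a scan schedule, since it includes baseline. Month 26 looks like a slip. Section 17 calls the study exploratory. The error rates need a rule that the plan never states, together with assumed correlations and retention. Most of the disagreement between months 24 and 60 is lost power: about 84–93% of discordant trials have month 24 significant and month 60 not.

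Much of this stands:

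- Month 24 is the natural reading.
- Inflation is conditional on counting any win.
- The larger figures come from the less favourable assumptions.
- The disagreement figure mainly describes a weaker late comparison, not a route to a false claim.
- Month 26 creates no rival result, because nothing can be reported there.
- The within-stratum question is separate from the time point, though the same sentence can settle it.

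The reply does not remove the contradiction. An implication drawn from other sections does not override an explicit primary endpoint list, and section 15.1 sets out to demonstrate an advantage at a time that it does not define.

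**Conclusion.** The concern holds and should be fixed. The conflict is between current sections of the protocol and does not depend on the amendment log. Month 24 is strongly implied, yet section 2.3 makes months 36 to 60 primary, section 15.1 tests five unranked visits, and section 16 names a month with no visit.

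Month 24 alone carries about a 5% false-positive rate. Counting any win raises it to about 6–9% (four visits) or 7–12% (five) with random slopes and full retention, to 11–12% or 12–15% with the assumed dropout, and to 13–17% or 15–20% under weaker correlation. The two-sided 0.05 level is inferred from section 16. The documents give no correlation or retention figure, so these are ranges under assumptions. The textual contradiction does not depend on them. The exploratory label lowers the stakes but does not say which result is primary.

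**What to change.** - **Sections 2.3 and 15.1:** name one primary comparison, the overall IVIG versus placebo difference in APCV at month 24, two-sided 0.05. Replace the end-of-study wording in the 15.1 aim with month 24.
- **Other visits:** list months 12, 36, 48 and 60 as secondary, in line with sections 2.1 and 2.2.
- **Strata:** state that within-stratum comparisons after a significant interaction support the primary result but do not replace it.
- **Section 16:** reconcile month 26 with the scheduled month-24 visit. The statement also powers mean volume while section 15.1 analyses APCV; that is a separate point, best corrected in the same edit.

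The change needs no new visits or data. The sponsor gives up claiming as primary a positive result at another visit or in one MCI stratum. Section 2.3 was widened by a deliberate amendment, and the Amendment 8 rationale shows that year-1 and year-2 conversions by MCI status had been seen. The change should therefore be dated and justified, with a statement of what was known at the time.

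Keeping every visit primary would cost more. With the back-solved SD, Bonferroni leaves per-visit power at 63–65% for four visits (alpha 0.0125) or 60–62% for five (alpha 0.01). From n = 2(z₁₋α/₂ + 0.915)² / 0.813², restoring 82% needs 2 × (2.498 + 0.915)² / 0.661 ≈ 36 per arm for four visits, or 2 × (2.576 + 0.915)² / 0.661 ≈ 37 for five.
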